- Radiographs (standing AP and lateral entire spine) completed within 6 months prior to intervention and
- DEXA scan of femoral neck\* (if applicable) completed within 24 months prior to enrollment and prior to intervention\*\* *UNLESS patient meets any of the following criteria, in which DEXA must be completed 12 months prior to intervention:*
  - Taking an FDA approved drug for the treatment of osteoporosis
  - History of fracture in the past year
  - Has taken Prednisone on a long term basis
  - Most recent DEXA scan t score was -2.5 or worse.

\*Waivers will be provided for patients meeting inclusion criteria who have had bilateral total hip replacements only if t score of spine and wrist are provided.

\* \**Patients enrolled in the NON surgical arm may initiate non-surgical treatment measures but must have DEXA completed (if required) within 3 month*

**Initial follow-up** is to be completed 30 to 120 days post intervention.

**Interim questionnaires/assessments** will be mailed and posted to database +/- 30 days of scheduled event (6, 9, 15, 18, 21, 30, 42, 72 months post intervention).

**One year follow-up** must be completed 11 months to 1 year 4 months post intervention.

**Two year follow-up** cannot be captured prior to 2 year anniversary date and up to 4 months post anniversary date.

**Three year follow-up** will be captured 2 year 11 months to 3 year 4 months post intervention.

**Four year follow-up** will be captured 3 year 11 months to 4 year 4 months post intervention. Patients who reach the 4 year milestone prior to end of current grant funding (Aug. 30, 2016) will be asked to sign a revised informed consent to include 5 year clinical visit and 72 month interim mailing if applicable).

**1.5.3 Patient Compliance:** To enhance patient compliance and participation, the site coordinators will mail interim questionnaires to all study participants at 6, 9, 15, 18, 21, 30, 42, & 72 months post-intervention. These will be completed in addition to the HRQOL questionnaires obtained at baseline and post-intervention clinical appointment visits (3, 12, 24, 36, 48 & 60 months). Furthermore, participants will be reimbursed for time and travel associated with completion of HRQOLs questionnaires, treadmill tests, radiographic and clinical exams.

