1.6.2 Sample Size Requirement: The experimental design is a 2bTrt (2 between-subjects factor levels: operative and non-operative) x 9wTime (9 within-subjects or repeated factor levels: 3-, 6-, 12-, 18-, 24-, 30-, 36-, 42-, and 48-month follow-up) factorial design. For the observational cohort study, the two treatment arms are not expected to be equivalent at baseline and, therefore, the data analysis is planned as a mixed-model longitudinal analysis with the change in SRS-QOL outcome at each follow-up point relative to baseline modeled from the baseline score and selected baseline covariates across time. Although follow-up times are fixed (as specified in the design), there is likely to be some variance in actual assessment times. Therefore, SRS-QOL outcome will be modeled by specifying a random intercept and basing the estimate on the date of assessment within each fixed follow-up assessment interval relative to the distance (in days) of the actual follow-up to the center point of the follow-up interval. In this way the longitudinal model includes both fixed (treatment and assessment period) and random (time deviation of assessment within each assessment period)

effects. The MIXED procedure in SAS Version 9.2 (SAS Institute, Cary, NC) will be used to evaluate these results and will provide overall all estimates of Treatment, Assessment Time and the Treatment x Assessment Time interaction effects. For the RCT group, although randomization at baseline is likely to diminish any baseline differences between the two groups, the same analysis approach will be followed. In this case, however, the covariates will be chosen based on their ability to explain and, therefore, help to compensate for possible attrition and/or crossover effects.

Sample sizes needed to achieve power of .80 for simple effects tests treatment differences at any given follow-up interval. Needed per group: 32-37 patients.

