Addendum 8/29/12: (modified and edited 6/19/13) The primary analysis plan for this study is to first evaluate the RCT and OBS studies separately using mixed model longitudinal regression analysis using an intent-to-treat approach. As was done in the SPORT analysis, assessment Intervals are treated as a fixed effect, meaning with each interval developed based on the date of intervention. Data gathered prior to date of intervention (DOI) will be considered baseline and fixed data points gathered after DOI will be classified according the form designation (e.g., 3mo, 6mo). Data points gathered after DOI that were not fixed points (e.g., complications, severe adverse events) will be associated with a fixed interval based on the length of time from the data point and DOI. A second random effects variable (Delta) will be created within each interval that reflects the distance (no. of days) between the actual observed point and the center of the fixed interval that this point falls within. Thus, patients may have multiple data points within a fixed interval and the distance orTime of data collection relative to DOI within each fixed interval will be included in the model. In addition, a Delta random variable, defined as the distance between the center of the fixed interval and the Time of data collect will, also be created. The primary analysis will regress the change in outcome (eg for the pcs outcome d_pcs) on baseline pcs (b_pcs), treatment, interval, site and patient age and sex,

For the RCT cohort, the base model for PCS would be

$$d_{\text{pcs}} = b_{\text{pcs}} \text{ treatment} | \text{interval} | \text{time site age sex}$$

A secondary analysis will replace time with the Delta variable with the model forcing the Delta covariate to have a value of 0 – thereby adjusting the results to reflect the expected value for the outcome as if the outcome was assessed at the exact center of the fixed interval.

$$d_{\text{pcs}} = b_{\text{pcs}} \text{ treatment} | \text{interval} \text{ delta site age sex} \text{ delta / delta} = 0$$

Where:

T_DOI = Date dependent variable was collected – DOI WITH negative T_DOI values indicating outcomes being assessed prior to treatment and positive T_DOI values indicating the time after DOI that the outcome was evaluated. Note that T_DOI values are nested within d_pcs
= -pcs-b_pcs (a positive change would reflect improvement)

b_pcs = baseline pcs

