Treatment = is a fixed effect with 2 levels the operative or non-operative care of the patient

Interval = is a fixed effect with X levels (depending on the outcome) indicating the follow-up times for collected patient outcomes

Time = The number of days between the date of assessment within an interval and the date of Intervention

site = the study site enrolling the patient (note site interactions may not be estimable in which case the interaction effects with site would be removed from the model)

age = a preplanned covariate

sex = a preplanned covariate

delta = a random effect reflecting the distance (in days) of the observed score in an interval from the center of the interval

Comparing the differences in these two modeling approaches may be useful for evaluating the relative merits of the two analysis approaches.,

For predictive modeling crossover will not be considered and as “Intent to treat” modeling – where the assigned treatment (in the RCT) or the selected treatment (in the OS) cohorts will be retained throughout the analysis.

Additional baseline covariates may be added to this model depending on the results of preliminary comparison of baseline differences between treatment groups and recursive partitioning methods will explore additional possible baseline factors and interactions among these factors to detect patient profiles that vary across treatment assignment. In addition, significant relationships between baseline variables and crossover status and loss to follow-up will also be useful for identifying covariates.

For the OBS group, where baseline differences between the two treatment groups are expected, the same basic model will be used and the same approach for adding covariates to the model based baseline differences between treatment groups, crossover status and loss to follow-up will be used.

The primary hypothesis of interest concerns differences between treatment outcomes at each time interval and differential change in outcomes within treatment across time intervals. Thus, preplanned follow-up simple effects tests associated with the treatment x interval interaction will be explored even if the interaction itself is not statistically significant (this is what preplanned means).

These simple effects tests will evaluate:

1. Differences in effect size (e.g. d_pcs) at each interval between the two treatment groups (e.g., are the effect sizes between treatment groups at 2 years significantly different?);

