2. Differences in effect sizes within each treatment group across the intervals (e.g. is the mean effect size for surgery at 3-months significantly different from the mean 6-month effect size?).
3. Differences in effect size change from one interval to the next between the treatment groups (e.g., are the slopes from 1 to 2 year follow-up significantly different across the two treatment groups?)

These analyses will

- a. Calculate a clinical trial p-value for each outcome at the 12- and 24-month time points
- b. Provide mean scores for each continuous outcome across all intervals, with conditional simple effects tests allowing for differential trajectories across time for the treatment groups.

Proc mixed in SAS version 12.1 64-bit running under the Windows 7 Ultimate 64-bit operating system will be used to analyze these data.

Evaluating Crossover. The exact approaches that will be used to handle crossover effects will depend on the magnitude and pattern of crossovers. Crossover in both the RCT and OBS studies will occur, and probably in both directions (non-op to surgery and surgery to non-op – meaning patients randomized or opting for surgery will never have the surgery).

Our approach for evaluating the effect of crossover would be to create a crossover variable to be included in the model that would have two possible values (0 – indicating no crossover; 1 – indicating crossover). By continuing with an Intent to treat philosophy for analysis, adding crossover status to the longitudinal regression modeling (along with interactions of crossover with treatment, interval and site) will provide a means for directly evaluating the effects that crossover will have in the model. Note that these models will be explanatory rather than predictive since crossover status will remain unknown until it occurs and, thus, is not a useful predictor. Including a crossover*treatment interaction will indicate (within each study cohort) who did and did not crossover and what the nature of the crossover was. Significant effects involving the crossover variables relative to outcomes and baseline characteristics, and interactions between the crossover variable and other

study factors (Treatment, Interval, Site) would be useful in determining what other covariates might be needed in the model to most accurately evaluate treatment efficacy across time. Our group at Dartmouth is considering using this approach for examining the effects of crossover in the SPORT trial as well.

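### The printed primary RCT model does not say at what time its 12- and 24-month treatment contrasts are evaluated; it also omits the Cobb randomisation stratum (minor)

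*SAP*

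**What the plan says.** The SAP addendum dated 8/29/12 (edited 6/19/13) sets out the primary model, using SF-12 PCS as its example. In prose, change is regressed "on baseline pcs (b_pcs), treatment, interval, site and patient age and sex"; time is not in that list. Just before, the addendum says that the "distance orTime of data collection relative to DOI within each fixed interval will be included in the model". The RCT formula then joins treatment, interval and time with bar operators and adds baseline score, site, age and sex. The definition is "Time = The number of days between the date of assessment within an interval and the date of Intervention", so it is not centred.

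A second model follows: "A secondary analysis will replace time with the Delta variable with the model forcing the Delta covariate to have a value of 0". Its formula enters delta as an additive term, yet the definitions read "delta = a random effect reflecting the distance (in days) of the observed score in an interval from the center of the interval". SAP 1.6.2 also measures timing from the centre of the follow-up interval and classes it as "random (time deviation of assessment within each assessment period".

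The planned outputs include: "Calculate a clinical trial p-value for each outcome at the 12- and 24-month time points". No time value is attached to them. Under Protocol 1.5.2 the two-year visit "cannot be captured prior to 2 year anniversary date and up to 4 months post anniversary date", and the one-year window runs from 11 to 16 months.

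Protocol 1.3 stratifies randomisation by site, age group, gender and Cobb severity (30-54° v 55-100°). The base model names site, age and sex. SAP 1.6.2 says the planning estimates were adjusted for Cobb angle, among other factors. The addendum allows further covariates chosen from the data, but does not name Cobb.

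**The concern.** Read as SAS notation, the bars give each arm its own straight line in time within each interval. The treatment difference at an interval is then a function of time and has no single value until a time is chosen. With raw days since intervention, nothing in the formula points to one. The SAP saw this need for the secondary model and fixed Delta at 0, but did nothing similar for the primary model.

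Two analysts with the same data and formula could therefore report different estimates, standard errors and p-values at the 2-year primary endpoint. SAP 1.6.2 powered the study on a plain difference between two groups at 2 years, with no within-window slope to estimate. The prose list, the formula and SAP 1.6.2 also describe timing in three different ways.

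The Cobb point is smaller: a randomisation factor that also fed the planning estimates has no pre-specified place in the model.

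**Working it through.** **1. The plan's own figures.** A two-sample t-test (two-sided 0.05, power 0.80) reproduces all six rows of Table 2: 24, 37, 64, 32, 50 and 87 per group. The row with means 0.3 and 0.8, SD 0.7 and N = 32 implies SE = 0.7 × √(2/32) = 0.175. The RCT closed at 63 patients (Addendum 1/17/13), so take 31 per arm: SE₀ = 0.7 × √(2/31) = 0.178.

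**2. Effect of the evaluation time, independent data.** In the crossed model, SE(t₀) = SE₀ × √(1 + ((t₀ − m)/s)²), where m and s are the mean and SD of visit time within the interval. Assume visits uniform over the window.

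- 24-month interval (24 to 28 months): m = 26, s = 4/√12 = 1.155. At nominal 24: √(1 + (2/1.155)²) = 2.00.
- 12-month interval (11 to 16 months): m = 13.5, s = 5/√12 = 1.443. At nominal 12: √(1 + (1.5/1.443)²) = 1.44.
- Overall mean time over the SAP's nine visits is 25.0 months. Multipliers: 1.33 for the 24-month interval and √(1 + (11.5/1.443)²) = 8.0 for the 12-month interval.
- At the interval's own mean visit day the multiplier is 1.

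**3. With repeated measures.** Generalised least squares, compound symmetry, nine visits, one assessment per interval, complete follow-up, 31 per arm. Correlation is 0.5, with the range for 0.3 to 0.7 in brackets:

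| Evaluation time | 24-month SE | 12-month SE |
|---|---|---|
| Interval's mean visit day | 0.18 | 0.18 (multiplier 1) |
| Overall mean time | 0.22 (0.23-0.20) | 1.10 (1.30-0.87) |
| Nominal month | 0.30 (0.33-0.26) | 0.23 (0.24-0.21) |

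**4. Power at 24 months** for Table 2's difference of 0.5, normal approximation:

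- Mean visit day: 0.5/0.178 = 2.81; Φ(2.81 − 1.96) = 0.80.
- Overall mean time: 0.5/0.215 = 2.33; Φ(0.37) = 0.64.
- Nominal 24 months: 0.5/0.297 = 1.68; Φ(−0.28) = 0.39.

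**5. Sensitivity.**

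- If annual visits bunch early (assumed Beta(1,3)), the nominal 24-month SE is 0.25 and the nominal 12-month SE is 0.18. At 26 months the SE is 0.26, so 24 months is then not the weak point.
- With 28 per arm (10% loss) and uniform visits, the nominal 24-month SE is 0.31.
- Overall mean time moves with the visits included: 13.9 months for protocol visits up to 24 months, and 28.8 for all fourteen. The independent-data multipliers at 24 months become 10.6 and 2.6.

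**6. Additive centred Delta.** The 24-month SE is 0.178 under every timing and correlation tried (0.187 with 28 per arm). With one slope common to both arms, the treatment contrast does not depend on the reference day. Treating Delta as a random slope instead (SD 0.02-0.20 per month) gives 0.178-0.184.

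**7. Cobb.** Divide the effect size by √(1 − R²). At partial R² of 0.02, 0.05 and 0.10 (assumed), N per group falls from 37 to 36, 35 and 33 (effect size 0.667) and from 32 to 32, 31 and 29 (0.714).

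**The case against.** A reader might infer that the primary analysis has only about 39% power because the SAP asks for results at 24 months. The documents do not support that. The addendum makes interval a categorical effect, assigns scheduled data by form label, and frames the tests as treatment differences within each interval. The 12- and 24-month points can equally mean those interval levels. Evaluated at each interval's mean visit day, the crossed model loses nothing. The prose list of primary terms omits time, so it is not even settled that the crossed model is the primary one.

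The size is uncertain too. The documents give neither the visit timing within windows nor the correlation. The formula is written for PCS, and SF-12 is collected only annually, whereas the calculation uses nine visits. The addendum allows several data points per interval. Addendum 1/17/13 reports SRS power of 0.995 at 12 months with 18 per group, an implied standardised effect of about 1.56 on a t-test approximation. An effect that large would survive an SE of 0.297: 1.56 × 0.7 = 1.09; 1.09/0.297 = 3.67; Φ(1.71) = 0.96. That figure rests on 26 patients and on 12 months, so it does not settle the 24-month question.

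Finally, the Delta model is already planned and is to be compared with the crossed one, so demoting the crossed model is partly a modelling preference.

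All of this stands against a claim of lost power. None of it supplies the missing evaluation time.

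**Conclusion.** The point holds as a gap in specification. As printed, the primary RCT model does not define its 12- and 24-month contrasts, and the three descriptions of timing do not agree. Under the assumptions above, the choice left open moves the 24-month SE between about 0.18 and 0.30. At 12 months, overall mean time would give about 1.1 and make the contrast useless. Whether any power is lost depends on the evaluation time used and on when patients attend, neither of which the documents fix.

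The Cobb omission is minor. A reader might infer bias from leaving out a stratification factor, but randomisation protects the comparison. Only a little precision is given up, and only if Cobb is prognostic.

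**What to change.** 1. Reconcile the addendum's prose, its formula and SAP 1.6.2 by using time centred within each interval (the Delta already defined) in the primary RCT model.
2. Enter Delta as a fixed covariate, as in the printed secondary formula. State that this replaces the random-effect label and assumes one within-window slope for both arms. That assumption is the small downside.
3. List each interval's reference day for reported arm means.
4. If the crossed model is kept, as primary or as a sensitivity analysis, state that its contrasts are taken at the interval's mean visit day and not at overall mean time.
5. Add the Cobb-severity stratum (30-54° v 55-100°) to the RCT base model as a pre-specified covariate.

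The cost is text only. The Delta model is already printed, Cobb severity is already recorded for randomisation, and no new data are needed. Relabelling Delta is a model change and should be declared as one, but it hardly alters the contrast's SE.

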Preliminary analyses prior to the longitudinal regression modeling will evaluate Treatment group differences at baseline in both the RCT and Observational cohorts in the RCT study, observed differences in HRQOL or personal demographics will evaluate the success of the randomization in the OBS study, observed differences in HRQOL and/or personal demographics will inform decisions regarding what covariates should be used to control for these baseline differences to allow better interpretation of longitudinal treatment differences. These analyses are likely to be done using recursive partitioning rather than stepwise regression methods, which, of late, have fallen into disfavor.

Sample size calculations to ensure adequate power were conservative by focusing on the ability to detect statistically significant differences between treatment groups at any specific follow-up interval. These are essentially a priori tests of simple effects of a treatment by time interaction, which is the primary focus of the study. These analyses are considered conservative for two primary reasons.

These differences are "between subjects" effects, meaning that the added power associated with repeated assessments across time do not help to increase power

The standard assumed standard deviations in the calculations did not consider the standard deviation estimate shrinkage likely to result from the included baseline covariates (mostly baseline outcome).

1.6.1 General Analysis Strategy: Our approach to data analysis includes three consecutive stages. Most analyses will be performed using SAS software, which has a wide range of statistical routines and offers great flexibility in data manipulation.

Stage 1 – Descriptive Analysis:

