Evaluating the statistical power for a mixed model longitudinal analysis is not straightforward. One conservative approach is to power the study with regard to a simple effects test associated with the highest order effect of interest in the study, here the Treatment x Assessment Time interaction. In this case, the sample size for the two treatment groups is estimated and, since the two treatment groups are not matched, the sample size per treatment group is likely to be larger than would be required to establish a significant change in outcome within a Treatment group across Assessment Time simple effects test (e.g., difference in SRS scores from baseline to 2-year follow-up). Accordingly, this study was powered with respect to the simple effects tests associated with a significant Treatment x Assessment Time interaction at the primary 2-year endpoint. This power analysis is informed by the data already gathered by the SDRG with the mean and standard error estimated adjusted for SRS baseline and patient age gender and Cobb angle. **Table 2 summarizes estimated sample sizes per treatment needed to achieve power of .80 for 2-tailed testing with type I error rate set at .05 under a variety of effect sizes, based on mean and standard deviation estimates.** The two rows highlighted were judged to reflect the most likely scenarios and, overall, the sample size of 30 per group in the RCT was considered a reasonable choice for achieving sufficient power to detect a real difference between the two treatment groups at 2-years follow-up.

Table 2

Estimated Means		Common SD	Effect Size	N per Group
Trt 1	Trt 2			
0.3	0.8	0.6	0.833	24
0.4	0.8	0.6	0.667	37
0.5	0.8	0.6	0.500	64
0.3	0.8	0.7	0.714	32
0.4	0.8	0.7	0.571	50
0.5	0.8	0.7	0.429	87

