From the study power analysis, power of 80% to detect an effect size between .667 - .714 with type I error rate set at .05 and 2-tailed testing requires a sample size of 32 – 37 patients per treatment group. We plan (are budgeted) to enroll 300 patients overall and expect about 100 (1/3) of these patients to be randomized. For the purposes of a stopping rule, N counts needed to establish power greater than 70 are more reasonable given stopping a study for futility is quite different than stopping rules associated with safety considerations. Power of 70% with an effect size of .667 requires 29 patients per group. A calculator estimating the probability of obtaining at least 58 patients from a sample of 300 enrolled patients under various recruitment and attrition scenarios

Based on this calculator results, futility risk (i.e., the inability to recruit at least 58 patients into the RCT) is quite high if, after 100 recruited patients, RCT recruitment is at no more than 20%, even if attrition rates are as low as 10%. When RCT recruitment rates are up to 25%, futility risks are relatively low when attrition rates are also low ($\leq 15\%$) but otherwise probability of successful recruitment are low. When RCT recruitment rates reach 30% for the first 100 enrollees, the probabilities of successful recruiting at least 58 patients is quite good, as long as attrition rates remain no greater than 30%.

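### The RCT primary model has a fixed core but an open, data-driven list of further covariates, and Cobb severity, a randomisation stratum, is left to that list

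*SAP*

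**What the plan says.** The addendum of 8/29/12 writes out the base model for the RCT with SF-12 PCS as the example. Change from baseline is regressed on the baseline score, treatment, interval, time, site, age and sex, and age and sex are described as preplanned. That part is settled.

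The same addendum then opens the model: "Additional baseline covariates may be added to this model depending on the results of preliminary comparison of baseline differences between treatment groups". Recursive partitioning is to search for further baseline factors and interactions, and "significant relationships between baseline variables and crossover status and loss to follow-up will also be useful for identifying covariates". The next paragraph gives the observational cohort the same approach, so the rule covers both cohorts.

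Two other places point the same way:

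- SAP 1.6.2, on the RCT: "the covariates will be chosen based on their ability to explain and, therefore, help to compensate for possible attrition and/or crossover effects".
- The Evaluating Crossover paragraph of the addendum lets significant crossover effects, including those on outcomes, inform which further covariates the efficacy model needs.

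SAP 1.6 says something different. In the RCT, "observed differences in HRQOL or personal demographics will evaluate the success of the randomization", while covariate choice from baseline differences is assigned to the observational study.

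Protocol 1.3 stratifies the randomisation by site, age group, gender and Cobb severity. SAP 1.6.2 names Cobb angle among the adjusters behind the power inputs. The base model contains site, age and sex but no Cobb term.

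**The concern.** A confirmatory model should be identifiable before anyone sees follow-up data by arm. Here the core is identifiable and the final model is not. The additions depend on observed arm differences, on crossover, on dropout and, through the crossover paragraph, on outcomes. The last three are known only after randomisation. Nothing states which variables are candidates, what counts as a difference, how many may enter, whether the selector is blinded, or when the choice is made.

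Three things follow:

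- **Precision.** Adjustment helps when a covariate predicts outcome. A chance difference between arms is a poor signal of that, so a rule triggered by imbalance usually leaves a useful covariate out.
- **Credibility.** An open list leaves room to choose the reported model after seeing its result, even if nobody intends to.
- **Design.** Cobb severity was important enough to stratify on, yet it enters the analysis only if a data-driven rule happens to select it.

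**Working it through.** **1. Reproduce the plan's figures.** The design is "power of .80 for 2-tailed testing with type I error rate set at .05". For two arms of n and standardised effect d, power is the probability that a noncentral t with 2n−2 df and noncentrality d·√(n/2) exceeds the two-sided 5% limits.

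- Row "0.3 0.8 0.7 0.714 32": 0.714 × √16 = 2.856, 62 df, power 0.803.
- Row "0.4 0.8 0.6 0.667 37": 0.667 × √18.5 = 2.869, 72 df, power 0.808.
- SAP 1.6.4, 29 per group: 0.667 × √14.5 = 2.540, 56 df, power 0.704 against the stated 70%.

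All six rows of Table 2 reproduce (24, 37, 64, 32, 50, 87). They are two-group calculations with no optional covariate, so the selection rule cannot make them wrong.

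**2. Sample size reached.** The addendum of 1/17/13 gives 63 randomised: 63/2 = 31.5, taken as 31 per arm. With the planned 10% loss, 63 × 0.9 = 56.7, or about 28 per arm.

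**3. One extra covariate, 31 per arm, d = 0.667.** Let r be its correlation with the outcome after the core has been fitted. Always adjusting raises the effective effect to d/√(1−r²). At r = 0.4 this is 0.667/√0.84 = 0.728, with noncentrality 0.728 × √15.5 = 2.87 and power of about 0.80. At r = 0 it is 0.667 × √15.5 = 2.63, with power of about 0.73. If the covariate is added only when its baseline comparison gives p < 0.10, randomisation triggers it in about one trial in ten, and the other nine keep the core model. Simulated power:

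| r (assumed) | added only if imbalanced | always adjusted |
|---|---|---|
| 0.1 | 0.72 | 0.72 |
| 0.2 | 0.72 | 0.73 |
| 0.3 | 0.74 | 0.77 |
| 0.4 | 0.75 | 0.80 |

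A separate run of 20,000 trials at r = 0.4 gave 0.736 with the core only, 0.744 if added on imbalance, and 0.801 if always adjusted. That is a loss of 5.7 points. The cut-off of 0.10 is an assumption: the SAP uses 0.10 only for Aim 2 screening and gives no cut-off here.

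**4. Six candidates, one prognostic, d = 0.714, 10,000 trials per cell.** R² is the share of residual variance that the prognostic covariate explains (assumed). Entries are percentages for R² = 0 / 0.1 / 0.2 / 0.3.

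| | 32 per arm | 28 per arm |
|---|---|---|
| Power, core only | 81.1 / 79.7 / 80.5 / 80.1 | 75.3 / 74.4 / 74.6 / 74.4 |
| Power, that covariate fixed | 80.3 / 82.9 / 88.1 / 91.1 | 74.4 / 78.1 / 82.5 / 87.1 |
| Power, selected on imbalance | 79.3 / 78.7 / 80.4 / 81.0 | 73.5 / 73.2 / 73.7 / 74.8 |
| Type I error, selected on imbalance | 4.9 / 4.4 / 4.2 / 3.6 | 5.3 / 4.8 / 4.2 / 3.9 |

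Selection on imbalance gives about the power of the core alone. Against the fixed prognostic covariate it loses about 4–10 points at 32 per arm and 5–12 at 28 for R² of 0.1 to 0.3. The loss is not universal: with R² = 0, fixing all six useless candidates gives 77.1% at 32 per arm, below the 79.3% from selection. Type I error is at or below nominal within Monte Carlo error (√(0.05 × 0.95/10,000) ≈ 0.2 points).

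**5. Hypothetical worst case.** If an analyst reported the smallest treatment p-value over all 64 subsets of the six candidates, type I error would be 8.5–11.7% at 32 per arm and 9.5–12.0% at 28.

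Selection on crossover or dropout was not simulated.

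**The case against.** The strongest reply is that most of the model is already fixed. Baseline score, site, age and sex are in the core, and SAP 1.6 expects most of the SD reduction to come from the baseline outcome. A reader might infer that all RCT covariates are picked after the fact. The documents do not support that: only the extras are open, and they are optional. This part of the reply stands.

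A reader might also infer that the stated power fails, or that the plan inflates type I error. Neither follows. The sample sizes do not rely on the extras, selection on imbalance did not raise the error rate, and no passage permits a search for the smallest p-value. The worst case in the working shows only what an open list cannot rule out.

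Nor does the rule adjust the primary model for crossover or dropout. The added variables are baseline variables, and models containing crossover status are labelled explanatory. Including baseline predictors of dropout can support the missing-at-random assumption of a likelihood-based mixed model. That is a good reason to keep such analyses, but not to leave the primary model's covariates undecided.

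Finally, baseline differences in the analysed set need not be pure chance. Protocol 1.3 removes patients lost before treatment together with their data, and Protocol 1.4 allows up to six months between assignment and surgery. This supports describing the arms at baseline. It does not turn an unstated imbalance threshold into a sound rule for adjustment.

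**Conclusion.** The concern holds in a limited form. The RCT primary model has a pre-specified core and an open list of additions governed by observed data, so the final confirmatory model is not fixed in advance. SAP 1.6 contradicts SAP 1.6.2 and the addendum on what RCT baseline comparisons are for. Cobb severity is the one stratification factor outside the core.

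The cost in power is conditional. At 31 per arm and d = 0.667 it is about 1 point or less for a correlation up to 0.2, and about 5–6 points at 0.4. It is larger only if a stronger predictor lies outside the core. The correlations, the number of candidates and the 0.10 cut-off are assumptions, so the documents do not settle the size. One further uncertainty concerns the planning SD. SAP 1.6 says it ignores covariate shrinkage, while SAP 1.6.2 says the inputs were adjusted for baseline score, age, gender and Cobb angle. If they were adjusted, part of the gain is already counted.

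The case for change rests on an unsettled confirmatory model and an easy remedy. It does not rest on a demonstrated error in power or in type I error.

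**What to change.** 1. State the RCT primary-model covariates as a closed list: baseline score plus the stratification factors (site, age, sex, Cobb severity), alongside the treatment and time terms already given. Cobb severity is the only new term.
2. Remove baseline imbalance, crossover and loss to follow-up as grounds for adding covariates to that model. Use covariates found that way, including baseline predictors of dropout, only in sensitivity analyses labelled as such.
3. Treat RCT baseline comparisons as descriptive.
4. Reconcile SAP 1.6, SAP 1.6.2, the covariate paragraphs of the 8/29/12 addendum and its crossover paragraph, so that they give one rule for the RCT. Data-driven covariate choice may stay for the observational cohort.

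The cost is SAP wording. All the variables are collected, and no sample size or visit changes.
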